8.7 CLASSIFICATION OF AN ADVERSE EVENT

8.7.1 Severity of Event

The intensity (severity) of AEs and SAEs will be graded according to a descriptive scale based on the National Cancer Institute Common Terminology Criteria for Adverse Events (CTCAE) Version 5.0

8.7.2 Relationship to Study Intervention

All adverse events (AEs) must have their relationship to study intervention assessed by the investigator who examines and evaluates the participant based on temporal relationship and his/her clinical judgment. The degree of certainty about causality will be graded using the categories below. In a clinical trial, the study product must always be suspect.

For all AEs and SAEs, the investigator will provide his best estimate of the causal relationship between the event and study drug, and the causal relationship between the event and study procedures. The degree of certainty about causality will be graded according to the following criteria.

- **Definitely Related** – There is clear evidence to suggest a causal relationship, and other possible contributing factors can be ruled out. The clinical event, including an abnormal laboratory test result, occurs in a plausible time relationship to study intervention administration and cannot be explained by concurrent disease or other drugs or chemicals. The response to withdrawal of the study intervention (dechallenge) should be clinically plausible. The event must be pharmacologically or phenomenologically definitive, with use of a satisfactory rechallenge procedure if necessary.
- **Probably Related** – There is evidence to suggest a causal relationship, and the influence of other factors is unlikely. The clinical event, including an abnormal laboratory test result, occurs within a reasonable time after administration of the study intervention, is unlikely to be attributed to concurrent disease or other drugs or chemicals, and follows a clinically reasonable response on withdrawal (dechallenge). Rechallenge information is not required to fulfill this definition.
- **Possibly Related** – There is some evidence to suggest a causal relationship (e.g., the event occurred within a reasonable time after administration of the trial medication). However, other factors may have contributed to the event (e.g., the participant's clinical condition, other concomitant events). Although an AE may rate only as "possibly related"

soon after discovery, it can be flagged as requiring more information and later be upgraded to “probably related” or “definitely related”, as appropriate.

- **Unlikely to be related** – A clinical event, including an abnormal laboratory test result, whose temporal relationship to study intervention administration makes a causal relationship improbable (e.g., the event did not occur within a reasonable time after administration of the study intervention) and in which other drugs or chemicals or underlying disease provides plausible explanations (e.g., the participant’s clinical condition, other concomitant treatments).
- **Not Related** – The AE is completely independent of study intervention administration, and/or evidence exists that the event is definitely related to another etiology. There must be an alternative, definitive etiology documented by the clinician.

8.7.3 Expectedness

For reporting purposes, the medically responsible investigator will be responsible for determining whether an adverse event (AE) is expected or unexpected. An AE will be considered unexpected if the nature, severity, or frequency of the event is not consistent with the risk information previously described for the study intervention.

Unexpected adverse events are those not listed in the Package Insert (P.I.) or Physicians’ Desk Reference (PDR), published medical literature, protocol, informed consent document or not identified. This includes adverse events for which the specificity or severity is not consistent with the description in the P.I. or PDR. For example, under this definition, hepatic necrosis would be unexpected if the P.I. or I.B. only referred to elevated hepatic enzymes or hepatitis.

For consistency of labeling and categorizing adverse events, the National Cancer Institute (NCI) Common Terminology Criteria for Adverse Events (CTCAE), Version 5.0 will be used in this study.

8.7.4 Time Period and Frequency for Event Assessment and Follow-Up

The occurrence of an adverse event (AE) or serious adverse event (SAE) may come to the attention of study personnel during study visits and interviews of a study participant presenting for medical care, or upon review by a study monitor.

All AEs including local and systemic reactions not meeting the criteria for SAEs will be captured on the appropriate case report form (CRF). Information to be collected includes event description, time of onset, clinician’s assessment of severity, relationship to study product (assessed only by those with the training and authority to make a diagnosis), and time of resolution/stabilization of the event. All AEs occurring while on study must be documented appropriately regardless of relationship. All AEs will be followed to adequate resolution.

Any medical condition that is present at the time that the participant is screened will be considered as baseline and not reported as an AE. However, if the study participant’s condition deteriorates at any time during the study, it will be recorded as an AE.

The severity of an AE will be documented at its highest level of severity. AEs characterized as intermittent require documentation of onset and duration of each episode.

Any time after informed consent is obtained, AEs and SAEs will be recorded and reported until 7 (for non-serious AEs) or 30 days (for SAEs) after the last day of study participation.

8.8 ADVERSE EVENT REPORTING

The occurrence of an adverse event (AE) or serious adverse event (SAE) may come to the attention of study personnel during study visits and interviews of a study participant presenting for medical care, or upon review by a study monitor.

All AEs including local and systemic reactions not meeting the criteria for SAEs will be captured on the appropriate case report form (CRF) and will be reported to the IRB according to the NIH-OHSRP Policy 801: *Reporting Research Events*. Information to be collected includes event description, time of onset, clinician's assessment of severity, relationship to study product (assessed only by those with the training and authority to make a diagnosis), and time of resolution/stabilization of the event. All AEs occurring while on study must be documented appropriately regardless of relationship. All AEs will be followed to adequate resolution.

8.8.1 Serious Adverse Event Reporting

Serious Adverse Events will be reported to:

- The NIH IRB according to NIH-OHSRP Policy 801: Reporting Research Events and Policy 802: Non-Compliance in Human Participants Research NIH-OHSRP Policy 801: Reporting Research Events and Policy 802: Non-Compliance in Human Participants Research, NIDCR Clinical Director's Office within 7 calendar days based on *NIDCR DIR Reporting* guidance.
- Pfizer Safety within twenty-four (24) hours of Institution's first awareness of an SAE, or immediately upon Institution's awareness if the SAE is fatal or life-threatening, according to Pfizer guidance and instructional material and templates. The study investigator will report to the Pfizer any serious adverse event, whether or not considered study intervention related, including those listed in the protocol or investigator brochure and must include an assessment of whether there is a reasonable possibility that the study intervention caused the event. Study endpoints that are serious adverse events (e.g., all-cause mortality) must be reported in accordance with the protocol unless there is evidence suggesting a causal relationship between the study intervention and the event (e.g., death from anaphylaxis). In that case, the investigator must immediately report the event to Pfizer.

All serious adverse events (SAEs) will be followed until satisfactory resolution or until the site investigator deems the event to be chronic or the participant is stable. Other supporting documentation of the event may be requested by Pfizer, if applicable and should be provided as soon as possible.

8.8.2 .Events of Special Interest

The following instances will be reported to Pfizer Safety as SAEs:

- Exposure to the Pfizer Product during pregnancy (see section 8.8.3) or lactation
- Drug overdose
- Medication error
- Occupational exposure to the Pfizer Product and
- Lack of effect of the Pfizer Product

- Potential drug-induced liver injury as assessed by if a Study subject develops abnormal values in aspartate transaminase (“AST”) or alanine transaminase (“ALT”) or both, concurrent with abnormal elevations in total bilirubin and no other known cause of liver injury, that event would be classified as a Hy’s Law Case.

8.8.3 Reporting of Pregnancy

This study includes pregnancy information as safety data and pregnancies will be recorded if they begin any time after enrollment. Information about any pregnancy should be reported promptly as SAE’s to Pfizer within 24 hours of the Institution becoming aware of the pregnancy according to Pfizer guidance and instruction and to the NIDCR Office of Clinical Director (OCD) within 7 working days; the DSMC will not receive an expedited report. All pregnancies identified during the study must be followed to conclusion and the outcome of each must be reported. The investigator should be informed immediately of any pregnancy in a study participant or a partner of a study participant. A pregnant participant should be instructed to stop taking study medication. The investigator should counsel the participant and discuss the risks of continuing with the pregnancy and the possible effects on the fetus. Tofacitinib has a pregnancy risk factor Category C; there are no adequate and well controlled studies in pregnant women. Pregnancy outcome should be determined and submitted to Pfizer Safety and the NIDCR, Office of Clinical Director. When possible, similar information should be obtained for a pregnancy occurring in a partner of a study participant. Should the pregnancy result in a congenital abnormality or birth defect Pfizer Safety and the NIDCR, Office of Clinical Director should be notified.

Sexually active participants with a partner able to become pregnant, will also be advised their partner should not become pregnant during study participation and 3 months following study completion. Participants and partners must agree to use effective birth control to be considered for study participation. The principal investigator or the medically responsible investigator will include discussion with participants or partners considering pregnancy after study participation during initial study participation discussions.

8.8.4 Unanticipated Problems (UP)

Definition of Unanticipated Problems (UP)

Any incident, experience, or outcome that meets all of the following criteria:

- Unexpected in terms of nature, severity, or frequency given (a) the research procedures that are described in the protocol-related documents, such as the Institutional Review Board (IRB)-approved research protocol and informed consent document; and (b) the characteristics of the participant population being studied; and
- Related or possibly related to participation in the research (“possibly related” means there is a reasonable possibility that the incident, experience, or outcome may have been caused by the procedures involved in the research); and
- Suggests that the research places participants or others (which many include research staff, family members or other individuals not directly participating in the research) at a greater risk of harm (including physical, psychological, economic, or social harm) than was previously known or expected.

Abbreviated Title: Tofacitinib in Sjögren's syndrome

Version Date: 07/01/2024

8.8.5 Unanticipated Problem Reporting

The investigator will report unanticipated problems (UPs) to the NIH Institutional Review Board (IRB) as per Policy 801.

9 STATISTICAL CONSIDERATIONS

9.1 STATISTICAL HYPOTHESIS

All analyses in this trial are descriptive and exploratory in nature. No formal statistical inferences are planned.

- Primary Endpoint(s): The primary objective is to evaluate the safety and tolerance of Tofacitinib in participants with SS. The primary endpoints include number and rates of adverse events (serious adverse events, Grade 3 and 4 toxicities not fulfilling the criteria for SAE, and non-serious adverse events) and number and rates of SS disease flares.
- Secondary Endpoint(s): Secondary endpoints will be analyzed by comparisons between the treatment (all SS participants receiving Tofacitinib) and placebo groups once the last participant completes the 28 weeks (196 days).
- Exploratory Endpoint(s):

For the following exploratory endpoints, all changes will be assessed between baseline and end of treatment, unless otherwise specified.

- Changes in salivary glands as assessed by histopathology including focus score, inflammation quantification and immunophenotyping of infiltrates
- Global transcriptomic changes in peripheral blood monocytes and minor salivary glands with specific interrogation of IFN regulated genes and other inflammatory pathways using software tools like Ingenuity Pathway Analysis.
- Differences between the treatment/placebo groups in changes in individual disease activity measures (ESSDAI, PGA, tear production, salivary flow) at the end of Study Day 168 will be analyzed as repeated measures with change from baseline as the dependent variable.
- Changes in participant reported outcomes such as: ESSPRI, SF-36, FSS, PROMIS
- Changes in non-invasive vascular studies
- A change will be analyzed using the appropriate statistical test per each type of data collected between baseline and at Day 168.

9.1.1 SAMPLE SIZE DETERMINATION

This is a pilot, Phase Ib-IIa study intended to study predominantly the tolerability/toxicity of Tofacitinib. The number of participants for this study is arbitrary and is based primarily on the conventional numbers in Phase II studies and our experience with similar studies conducted previously. The primary endpoint is safety and tolerability. 15- 20 participants are commonly used as the sample size for open label safety studies. Our plan to have 20 Participants dosed with Tofacitinib to evaluate for safety and a placebo group of additional 10 participants for comparison is consistent with Phase I studies.

9.2 POPULATIONS FOR ANALYSES

9.2.1 Safety Population

All participants who receive at least one dose or part of a dose of the study intervention and complete a safety follow-up, whether withdrawn prematurely or not, will be included in the safety population. All data relating to safety will be listed and summarized separately for the treatment period and for the entire study. All safety reports will be reviewed by the Principal Investigator.

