7.2 PARTICIPANT DISCONTINUATION/WITHDRAWAL FROM THE STUDY

Prior to removal from study, effort must be made to have all subjects complete a safety visit approximately 14 days (+14 days) following the last dose of study therapy. Participants are free to withdraw consent at any time upon request. Participants may also choose to withdraw treatment but remain in the study for follow up. Participants must be withdrawn consistent with Section 6.1.2. Additionally, the PI or Medically Responsible Investigator may also choose to withdraw treatment or withdraw a participant from the study based on clinical or professional judgement. An investigator may withdraw treatment or a participant from study for the following reasons:

- Request by participant to be withdrawn from the study.
- Flares not resolving within 28 days or if, in the opinion of the medically-responsible investigator, the participant requires immediate immunosuppressive therapy that is not allowed in the protocol.
- Any Grade 4 adverse event that is unexpected and at least possibly related to study drug.
- More than 45 days delay in treatment after the screening visit.
- More than one (1) "no-show" for a visit.
- Persistent elevation of LFTs of > 2 times upper limit of normal persistently present on repeated samples 14 days +/- 7 days apart.

- >30% increase in serum creatinine from baseline at enrollment, persistently present on repeated samples 14 days +/- 7 days apart.
- Increase in proteinuria at the time of screening visit to protein to creatinine ratio of more than 1.000 mg/dL or more than 1000 mg in a 24 hours urine collection, persistently present on repeated samples 14 days +/- 7 days apart.
- Any other reason that, in the opinion of the responsible Investigator or Medically Responsible Physician, poses unacceptable risk to the participant.
- Infections requiring intravenous antibiotic treatment.
- Development of any malignancy.
- Urine BK virus level of more than 10 million copies/ml by quantitative PCR or detection of BK virus in serum by quantitative PCR.
- Non-compliance with treatment (<80% compliance by pill count).

The reason for participant discontinuation or withdrawal from the study will be recorded on the Voluntary Study Withdrawal Case Report Form (CRF). Participant who signs informed consent and are randomized, but do not receive the study drug, may be replaced.

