While on this study, participants will continue to receive regular medical care from their primary physicians. Any AEs reported will be followed by the investigators as described in Section 16.1.8. Following completion of the study or after withdrawal from the study, participants will return to the care of their referring physicians. Participants may continue their follow up visits on protocol 15-D-0051 as appropriate. A summary of the participants' course in the study will be sent to the referring physician.

Participants who withdraw or are withdrawn from the study after receiving study treatment will be asked to complete the day 168 and 196 for close out safety assessments. Participants are deemed ineligible before study day 1 or randomization will resume care with their referring physician with no further evaluation in this protocol.

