8.2.5 Adverse event assessment

Adverse events will be assessed by reviewing the interim medical history, performing a physical evaluation, asking open-end question of how the participant's feeling and reviewing laboratory results at each visit, as well as part of the clinical monitoring telephone calls on study days 7, 21, 42, 70, and 154 (+/- 3 days) as per Section 5.1.2.. After completing screening assessments, any adverse event (AE) or serious adverse event (SAE) reported by a subject, whether or not study drug has been administered, will be recorded by the investigators. Any AE/SAE prior to dosing will be categorized as "Baseline" and any AE/SAE after dosing will be categorized as "treatment-emergent."

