8.5 SAFETY AND OTHER ASSESSMENTS

Patient safety will be assessed through clinical assessments and laboratory studies during scheduled follow up visits (SOA), symptom assessment during interim phone calls (SOA), and assessment of AEs.

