9.2.2 Intent to Treat Population

Anyone randomized and receiving at least one dose of study drug will be included in the intent to treat population.

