9.2.3 Toxicity Evaluation

All participants will be evaluable for toxicity from the time of their first dose of study drug, Tofacitinib 5 mg, orally, twice daily.

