9.3.2 Analysis of the Primary Endpoints

The primary goal is to evaluate the safety and tolerance of Tofacitinib in participants with SS. For the safety population, the number and percentage of subjects with any AE, any related AE, any SAE, any Grade 3 and 4 toxicities not fulfilling the criteria for SAE, and non-serious adverse events and SS disease flares, as well as the total number of events for each category will be summarized by treatment group. AE's/SAE's will be reported from the time of consent. Events that are reported prior to the first treatment will be considered non-treatment emergent in analyses.

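### Entry to the safety population for the primary endpoint depends on completing an undefined follow-up after dosing, so treated participants can drop out of the toxicity percentages

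*Combined protocol and SAP*

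**What the plan says.** The primary analysis in 9.3.2 is set on one population: "For the safety population, the number and percentage of subjects with any AE", followed by related events, serious events, Grade 3 and 4 toxicities and flares, all by treatment group.

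Section 9.2.1 defines that population by two conditions. The participant must have taken at least part of a dose, "and complete a safety follow-up, whether withdrawn prematurely or not, will be included in the safety population".

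The two neighbouring definitions have no second condition:

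- 9.2.2: "Anyone randomized and receiving at least one dose of study drug will be included in the intent to treat population".
- 9.2.3: "All participants will be evaluable for toxicity from the time of their first dose of study drug".

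The follow-up in 9.2.1 is not defined. Other sections offer several candidates:

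- 7.2, before removal from the study: "effort must be made to have all subjects complete a safety visit approximately 14 days (+14 days) following the last dose".
- 8.2.2, participants withdrawn after treatment: "will be asked to complete the day 168 and 196 for close out safety assessments".
- 8.2.5, adverse events are assessed at each visit, "as well as part of the clinical monitoring telephone calls on study days 7, 21, 42, 70, and 154".
- 8.5, safety is assessed "during scheduled follow up visits (SOA), symptom assessment during interim phone calls (SOA), and assessment of AEs".

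Section 8.2.11 also mentions safety visits, without timing.

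**The concern.** The denominator of the primary endpoint, and part of its numerator, depends on something that happens after treatment starts. Completion is not assured: 7.2 asks only for an effort, 8.2.2 only makes a request, and 7.3 plans for participants who cannot be reached. Nor is missing the follow-up clearly unrelated to harm. Several withdrawal reasons in 7.2 are themselves safety events, such as infections needing intravenous antibiotics, malignancy and persistent liver enzyme elevation.

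The safety set can therefore be smaller than the intent-to-treat set, and no section says how a treated participant without the follow-up is counted. At stake are the reported toxicity percentages and the comparison between arms of 20 and 10. Section 4.2 says these data may be used to design and power a larger study.

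**Working it through.** **What each reading of the follow-up excludes**

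| Reading | Source | Treated participants who leave the primary percentages |
|---|---|---|
| (a) Visit about 14 days after last dose | 7.2 | Those who die or are lost before that visit |
| (b) Day 168 and 196 close-out assessments | 8.2.2 | Those who die or are lost before close-out |
| (c) Any safety contact after dosing, from the Day 7 call | 8.2.5, 8.5 | Only those with no contact after dosing |

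The words in 9.2.1 about premature withdrawal suggest an intent to keep early leavers. Grammatically, though, the follow-up condition applies to them as well.

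**Inputs**

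- Planned arms are 20 tofacitinib and 10 placebo (4.1).
- Expected withdrawal is about 25%, with 30 + 11 = 41 enrolled (7.2). As a check, 30/(1 − 0.25) = 40, one below the stated 41; 4.1 says the extra places also serve to complete unfilled randomization blocks. The 25% is withdrawal, not missed safety follow-up.
- The documents give neither a toxicity rate for this population nor a rate of missed follow-up. The counts below are assumptions.

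**Formula**

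Let x of n treated participants have toxicity, e be excluded, and k of those excluded have toxicity. The reported rate is (x − k)/(n − e). It is below x/n when n(x − k) < x(n − e), that is, when k/e > x/n. It is above x/n when k/e < x/n.

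**Tofacitinib, assumed 2/20 = 10.0%**

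| Excluded (e) | With toxicity (k) | Reported rate |
|---|---|---|
| 1 | 1 | 1/19 = 5.3% |
| 1 | 0 | 2/19 = 10.5% |
| 2 | 2 | 0/18 = 0.0% |
| 2 | 1 | 1/18 = 5.6% |
| 2 | 0 | 2/18 = 11.1% |
| 5 | 2 | 0/15 = 0.0% |
| 5 | 1 | 1/15 = 6.7% |
| 5 | 0 | 2/15 = 13.3% |

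Five excluded is 25% of 20. It is an upper-end illustration that treats every withdrawal as a missed follow-up.

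**Placebo, assumed 1/10 = 10.0%**

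One exclusion gives 0/9 = 0.0% or 1/9 = 11.1%.

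**Larger treated set**

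If all 41 places are used and dosed, about 41 × 2/3 = 27 are on tofacitinib. Then 2/27 = 7.4% becomes 1/26 = 3.8% or 2/26 = 7.7% with one exclusion.

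**Expected effect at an assumed true rate p = 10%**

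Let q1 be the probability of missing follow-up with toxicity and q0 without. The expected reported proportion is about p(1 − q1)/[p(1 − q1) + (1 − p)(1 − q0)].

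- q1 = 0, q0 = 0.25: 0.100/0.775 = 12.9%
- q1 = q0 = 0.25: 0.075/0.750 = 10.0%, no bias
- q1 = 0.25, q0 = 0.05: 0.075/0.930 = 8.1%
- q1 = 0.50, q0 = 0.05: 0.050/0.905 = 5.5%

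**Precision**

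Clopper-Pearson 95% intervals are 1.2–31.7% for 2/20, 0.1–26.0% for 1/19 and 1.7–40.5% for 2/15. They overlap widely.

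**The case against.** The strongest reply is that reading (c) is the natural one. Section 9.2.1 asks for a follow-up, not a particular visit, and expressly mentions early leavers; 8.5 counts visits and calls as safety assessment. On that reading the rule removes only people with no safety information after dosing. That is a fair account of what may have been intended, but the plan does not say it, and the other readings have direct support in 7.2 and 8.2.2.

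Three further points limit the size without removing the problem:

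- **Follow-up of events.** Sections 8.7.4 and 8.8 commit to following adverse events to resolution, so participants with toxicity may be the least likely to be missed. This makes the downward cases less likely. It does not cover death or loss of contact before the qualifying visit under (a) or (b).
- **Listing of all safety data.** The next sentence of 9.2.1 promises to list and summarize all safety data. It does not settle the denominator of the percentages in 9.3.2.
- **Scope of 9.2.3.** It can be read as stating when evaluability starts, not who belongs to an analysis set. Even so, its statement that everyone is evaluable does not fit a rule that drops some treated participants, and the mismatch with 9.2.2 remains.

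It is also true that 9.1 plans no formal inference, that the counts above are assumed, and that there is no expected bias if missed follow-up is unrelated to toxicity.

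**Conclusion.** The concern holds. As written, 9.2.1 makes membership of the primary analysis set depend on an undefined assessment after dosing, which conflicts with 9.2.3 and lets the safety set be smaller than the intent-to-treat set. The bias can go either way. In the assumed 2/20 case, excluding one participant with toxicity lowers the percentage by 4.7 points, while excluding one without raises it by 0.5. Under reading (c) the effect would be small. No direction is established, because the documents do not say who would miss the follow-up. No type I error rate or power is affected, and individual events remain captured and reported. This should be fixed because it concerns the primary endpoint's definition and should not be left to be settled after unblinding.

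**What to change.** Delete the follow-up condition from 9.2.1, so that the safety population is every participant who received at least one dose or part of a dose, in line with 9.2.3. Add a sentence that withdrawn and replaced participants stay in all safety numerators and denominators. Report by arm how many treated participants lack the post-treatment safety visit.

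The cost is one deleted clause, one added sentence and one extra table line, with no new data collection. Participants with short observation will enter the denominator, and reported toxicity may look slightly less favourable.

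Two housekeeping corrections can go in the same edit, though the conclusion does not rest on them. Section 9.3.4 refers safety analyses to 9.2.2 and should point to 9.3.2. The two statements in 7.2 on replacing participants who withdraw after dosing differ in scope and should be reconciled.
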